##### 2. Worst-Likely-Case Scenario for Missing Data

- o For patients missing baseline quality of life, set the baseline quality of life equal to the mean baseline value for the appropriate stratum of the population. Population to be stratified based on type of surgery (cardiac versus non-cardiac) and history of falls.
- o For patients in the control group missing one-year quality of life, set the quality of life value equal to the maximum postoperative quality of life within the patient's stratum (still stratified by type of surgery and history of falls).

- For patients in the intervention group missing one-year quality of life, set the quality of life value equal to the minimum postoperative quality of life within the patient's stratum (still stratified by type of surgery and history of falls).
- Patients who die before one year will be excluded.

3. Expanded Control Group with Matched Cohort

- Each patient randomized in the ENGAGES trial will be matched to a patient enrolled in the SATISFY-SOS study.
  - All patients enrolled in SATISFY-SOS who meet the following criteria will be considered.
    - Age 60 or older
    - Hospital stay  $\geq$  2 days
    - Surgery between January 2015 and May 2018 (same dates as ENGAGES)
  - For each patient meeting the above criteria, a propensity score for enrollment in the ENGAGES trial will be constructed using logistic regression. Covariates included in the model will include age, sex, ASA physical status, surgery type (cardiac versus non-cardiac), and history of falls.
  - (Because all patients enrolled in ENGAGES were co-enrolled in SATISFY-SOS, the population described above will include all patients who were enrolled in ENGAGES.)
  - Patients enrolled in ENGAGES will be matched 1:1 without replacement to SATISFY-SOS patients not enrolled in ENGAGES based on the logit of the propensity score. A greedy nearest-neighbor algorithm will be used, with a maximum caliper width of  $0.2 * \text{the standard deviation in the logit of the propensity score}$ .
  - Use the same model structure described above.
  - Add a variable to Z indicating whether the patient was enrolled in ENGAGES.

4. Patient-Reported Subjective Quality of Life Change

- Analysis to include the subset of patients enrolled in ENGAGES who returned the SATISFY-SOS survey at one year
  - The survey includes a question asking if quality of life is better, the same, or worse compared to before surgery

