***Hypothesis 3: Is EEG Guidance Intervention Associated with Fewer Falls One Year After Surgery?***

*Patient Population:* Patients randomized to intervention or control (N = 1232)

*Primary Predictor Variable:* EEG guidance intervention

(X=0 for control or X=1 for intervention)

Intention to treat

*Outcomes:* Presence or absence of fall(s) during the one-year postoperative follow-up period, measured via patient report one the one-year ENGAGES survey

- Patients who did not fill out the survey (including both living non-respondents and deceased patients) will be excluded

*Data Description Plan:* Confusion matrix of falls versus EEG guidance intervention

*Analysis Plan:* Logistic regression

- Will perform unadjusted and adjusted analyses
- Will adjust for age, sex, American Society of Anesthesiologists (ASA) physical status classification (1-3 vs 4-5), number of comorbid conditions, history of falls (yes/no within previous 6 months), evidence of abnormal cognition (preoperative Short Blessed Test score > 4), surgery type (cardiac versus non-cardiac), length of anesthesia (Anesthesia Stop – Anesthesia Start)
  - o Note that ASA is dichotomized in this analysis, and functional capacity <4 METS has been dropped. These changes were made to reduce the number of degrees of freedom in the model, with the goal of having one degree of freedom per 10 patients who fell.
  - o Multiple imputation may be used to address missing values of these variables

*Planned Sensitivity Analyses*

1. Deceased Patients
  - o Assume all patients who die within one year have fallen.
2. Best-Case Scenario for Missing Data
  - o Assume all patients who die within one year have fallen.
  - o Assume that living patients in the intervention group with missing fall outcome data have not fallen. Assume that living patients in the control group with missing fall outcome data have fallen.
3. Worst-Case Scenario for Missing Data
  - a. Assume all patients who die within one year have fallen.
  - b. Assume that living patients in the intervention group with missing fall outcome data have fallen. Assume that living patients in the control group with missing fall outcome data have not fallen.
4. Expanded Control Group with Matched Cohort
  - o Use the same matched cohort as described above in Hypothesis 2.
  - o Perform a logistic regression as described above, also adjusting for whether the patient was enrolled in ENGAGES.
5. Number of Falls

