  - o For patients who completed the SATSIFY-SOS 1-year survey, we have a categorical variable detailing the number of falls (0, 1, 2, or 3+).
  - o Perform an ordinal logistic regression, adjusting for the variables described above.

*Exploratory Analyses:*

1. Is duration of intraoperative EEG suppression (minutes with suppression ratio > 1%) associated with mortality?
  - a. Cox proportional hazards model, adjusting for same variables as in hypothesis #1
  - b. Instrumental variable analysis will be used to account for the EEG intervention

2. Is duration of intraoperative EEG suppression (minutes with suppression ratio > 1%) associated with worse quality of life at one year?
  - a. Generalized linear model, same structure as in hypothesis #2
  - b. Instrumental variable analysis will be used to account for the EEG intervention
3. Is duration of intraoperative EEG suppression (minutes with suppression ratio > 1%) associated with more falls at one year?
  - a. Logistic regression, adjusting for same variables as in hypothesis #3
  - b. Instrumental variable analysis will be used to account for the EEG intervention
4. Is duration of intraoperative BIS < 40 associated with mortality?
  - a. Cox proportional hazards model, adjusting for same variables as in hypothesis #1
  - b. Instrumental variable analysis will be used to account for the EEG intervention
5. Is duration of intraoperative BIS < 40 associated with worse quality of life at one year?
  - a. Generalized linear model, same structure as in hypothesis #2
  - b. Instrumental variable analysis will be used to account for the EEG intervention
6. Is duration of intraoperative BIS < 40 associated with more falls at one year?
  - a. Logistic regression, adjusting for same variables as in hypothesis #3
  - b. Instrumental variable analysis will be used to account for the EEG intervention
7. Is median intraoperative end-tidal anesthetic concentration value (measured in MAC) associated with mortality?
  - a. Cox proportional hazards model, adjusting for same variables as in hypothesis #1
  - b. Instrumental variable analysis will be used to account for the EEG intervention
8. Is median intraoperative end-tidal anesthetic concentration value (measured in MAC) associated with worse quality of life at one year?
  - a. Generalized linear model, same structure as in hypothesis #2
  - b. Instrumental variable analysis will be used to account for the EEG intervention

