iii) Falls (Aims 2 and 3 in Figure 2)

In the baseline (preoperative) questionnaire for the SATISFY-SOS study, patients are asked to indicate how many times they fell during the past 6 months and injuries from falls are ascertained. Patients who fell at least one time during the past six months will be classified as having a previous history of falls. On the 30-day and 1-year follow-up postoperative questionnaires, patients are asked to indicate whether they have experienced a fall. Based on this information, we will define two outcomes measures: Falls within 30-days and falls within 1-year of surgery. Data on number of falls and injurious falls will also be collected. The wording for the falls questions used in SATISFY-SOS is based on the definition proposed by the Prevention of Falls Network Europe (ProFaNE); the calculation for severity of fall is based on a standard algorithm.⁹⁸⁻¹⁰⁰

Pre-specified additional analyses and sub-studies

The primary aim of the ENGAGES study is to determine whether an EEG-guided anesthetic protocol can decrease postoperative delirium and its associated downstream negative sequelae (e.g., decrement in quality of life, falls). However, it is important that large, randomized trials collect and report data on multiple clinically relevant outcomes to maximize scientific yield and efficiency. The ENGAGES trial will have the potential to

Patient Centered Approach

Several aspects of the ENGAGES study are patient centered in their conception. There is a community liaison group that has been actively involved in the design and in the conduct of the study. Important outcomes in the study are based on patient reported outcomes measures. Both patients and their families are provided with educational material on delirium, its risk factors and its sequelae. The study also includes patient self-assessment for delirium and implementation of the validated Family Confusion Assessment Method (FAM-CAM)^{103,104} instrument both in hospital and after hospital discharge. Both of these will be included in pre-specified sub-studies of the ENGAGES trial (see addendum).

Statistical Analyses

i) Effectiveness of EEG-guided anesthesia protocol in reducing incident postoperative delirium compared with usual anesthetic care (Aim 1 in Figure 2)

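### The main one-year falls analysis drops patients without the ENGAGES survey even when their one-year falls status is on the SATISFY-SOS survey, and the missing-data scenarios can overwrite a recorded fall

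*SAP*

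**What the plan says.** **Main outcome (SAP, Hypothesis 3, Outcomes).** The outcome is "Presence or absence of fall(s) during the one-year postoperative follow-up period, measured via patient report one the one-year ENGAGES survey". The rule for everyone else is: "Patients who did not fill out the survey (including both living non-respondents and deceased patients) will be excluded".

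**Second one-year source (SAP, Hypothesis 3, sensitivity analysis 5).** "For patients who completed the SATSIFY-SOS 1-year survey, we have a categorical variable detailing the number of falls (0, 1, 2, or 3" or more). An ordinal logistic regression is fitted to this variable with the Hypothesis 3 covariates.

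**Who has the second source (SAP, Hypothesis 2, sensitivity analyses 3 and 4).** The matching step gives the overlap of the two studies: "Because all patients enrolled in ENGAGES were co-enrolled in SATISFY-SOS". The SAP does not expect every patient to return the SATISFY-SOS form. The subjective quality-of-life analysis is restricted accordingly: "Analysis to include the subset of patients enrolled in ENGAGES who returned the SATISFY-SOS survey at one year".

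**Missing-data scenarios (SAP, Hypothesis 3, sensitivity analyses 2 and 3).** Living patients with missing fall data are assigned fallen or not fallen according to arm. No exception is made for a fall reported on another survey.

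**Protocol (Outcome Measures, iii Falls).** "On the 30-day and 1-year follow-up postoperative questionnaires, patients are asked to indicate whether they have experienced a fall". It continues: "Based on this information, we will define two outcomes measures: Falls within 30-days and falls within 1-year of surgery". It also ties the question wording to SATISFY-SOS: "The wording for the falls questions used in SATISFY-SOS is based on the definition proposed by the Prevention of Falls Network Europe".

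The SAP contains no rule for combining or reconciling these sources, and it uses the 30-day falls report nowhere.

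**The concern.** Falls at one year are a key secondary outcome, and survey non-response is the main threat to it. The SAP treats the ENGAGES and SATISFY-SOS one-year surveys as separate instruments that reach the same randomised patients. Two consequences follow if the text is applied as written.

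1. A patient who returned the SATISFY-SOS form but not the ENGAGES form is excluded from the main analysis, although one-year falls status is known.
2. The same patient enters the best- and worst-case scenarios as missing. In the best case, a living intervention patient with a recorded fall is set to not fallen. In the worst case, this happens to a living control patient. A recorded absence of falls can equally be overwritten with a fall. A bounding analysis should vary only what is unknown.

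The losses are precision, bounds that are wider than the data require, and scenario results that contradict data the sponsor holds.

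**Working it through.** **Inputs**
- Randomised: 1,232, 1:1 (SAP, Hypothesis 3; protocol, Randomization and Blinding).
- Control falls 40%, reduction 12 points, about 1,000 patients (roughly 80%), two-sided 0.05, power above 80% (protocol, Sample Size Calculations, iii).
- One-year response seen in SATISFY-SOS: about 66% (protocol, Strengths and Limitations). Applying it to the ENGAGES survey is an assumption.
- Share of randomised patients with a SATISFY-SOS one-year form but no ENGAGES form: not given. Assumed range 0% to 15%. Zero is possible if the SATISFY-SOS responders all returned the ENGAGES form too.
- Effect of 8.5 points (40% versus 31.5%): not a protocol figure. It is the difference that 1,000 patients detect with about 80% power, used here to show a case where sample size matters.

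**Formula.** Two proportions, n per arm, p̄ = (p1 + p2)/2:

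power = Φ( [ |p1 − p2| − 1.96·√(2p̄(1 − p̄)/n) ] / √( [p1(1 − p1) + p2(1 − p2)]/n ) )

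**Step 1: the protocol's own figure.** n = 500, 40% versus 28%, p̄ = 0.34. The critical difference is 1.96·√(2 × 0.34 × 0.66/500) = 0.0587. The standard error is √((0.24 + 0.2016)/500) = 0.0297. Power = Φ((0.12 − 0.0587)/0.0297) = Φ(2.06) = 98.0%. The stated lower bound of 80% holds.

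**Step 2: patients recovered.** 0.66 × 1,232 = 813; 0.71 × 1,232 = 875; 0.81 × 1,232 = 998.

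| Recovered (share of randomised) | N | Power, 12 points | Power, 8.5 points |
|---|---|---|---|
| 0% | 813 | 95.2% | 71.6% |
| 5% | 875 | 96.4% | 74.7% |
| 15% | 998 | 98.0% | 80.1% |

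At the protocol's 80% return (0.80 × 1,232 = 986), power before any recovery is already 97.9% for 12 points and 79.6% for 8.5 points.

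**Step 3: width of the best-to-worst range.** Let m be the missing share in each arm, ignoring deaths. Moving from the best to the worst case changes the assigned rate by m in each arm, so the risk difference spans 2m. At 66% return, m = 34% and the span is 68 points. Recovering 5% of randomised patients gives 2 × 29 = 58 points, and recovering 15% gives 2 × 19 = 38 points. With no recovery it stays at 68.

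**Step 4: known falls in the scenarios.** This needs no arithmetic. An intervention patient is alive, has no ENGAGES form, and reports two falls on the SATISFY-SOS form. That patient is absent from the main analysis, counted as not fallen in the best case, and counted in the two-fall category in sensitivity analysis 5. The three entries cannot all describe the same patient.

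**The case against.** **The SATISFY-SOS falls are not ignored.** Sensitivity analysis 5 is a planned treatment comparison on that survey. This stands. It is a separate ordinal model among that survey's own responders, however, and does nothing for the main outcome or the scenarios.

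**One uniformly collected source is a defensible choice.** This also stands in part. A single instrument avoids mixing sources, and a rule that counts any positive report makes detection depend on how many forms a patient returned, which is a post-randomisation event. For that reason the fix below does not put such a rule in the main analysis.

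**The gain may be nil.** The documents do not give the overlap between the surveys, so no recovery at all is possible, and the protocol plans extra telephone follow-up. This stands, and the range above starts at zero. The scenario rules would still need the exception for 30-day falls.

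A reader might go further and infer three things that the documents do not support:

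- *That the SAP contradicts a pooled protocol definition.* The protocol names two questionnaires and two outcomes. Reading each outcome from its own questionnaire is at least as natural as combining them, and no any-positive rule is stated.
- *That known early fallers are misclassified in the main analysis.* The one-year question is meant to cover the whole year. An error needs a patient who fell early to answer no later, and no rate is given. If the question detected 80% of fallers equally in both arms, with no false positives, the 12-point difference would shrink to 9.6 points and power with 1,000 patients would still be 92.8%.
- *That the trial is underpowered for falls.* At 813 patients, power for the protocol's effect is 95.2%.

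**Conclusion.** The point holds in limited form. Read as written, SAP Hypothesis 3 excludes patients whose one-year falls status may be on file, and its best- and worst-case rules can replace an observed status with the opposite one. Both follow from the text alone.

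The size is uncertain. Under an assumed 66% return and 0% to 15% recovery, N rises from 813 to at most about 998. Power for 12 points moves from 95% to 98%, and for an assumed 8.5 points from 72% to 80%. Ignoring deaths, the best-to-worst span falls from 68 points to no less than 38. The case therefore rests on using observed outcomes and on interpretable bounds; power matters only for effects smaller than the protocol's. This is an inexpensive improvement to a key secondary analysis and does not invalidate it.

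**What to change.** In SAP Hypothesis 3:

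1. **Main outcome.** Use the ENGAGES one-year answer where present. Otherwise use the SATISFY-SOS one-year answer, coded 0 versus 1 or more falls. Exclude only patients with neither.
2. **Best- and worst-case scenarios.** Keep any fall or no-fall status observed on either one-year survey. Count a fall reported at 30 days as a fall. Assign by arm only what remains unknown. A 30-day report of no fall does not settle the year and should not be used as a no.
3. **Sensitivity analyses.** Add the ENGAGES-only definition. Add an any-positive-report definition that includes 30-day falls, restricted to patients with a one-year survey, so that 30-day reports can reclassify patients but not select them into the analysis.
4. **Reporting.** Tabulate by arm how many patients have each survey and how well the surveys agree.

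The cost is a few lines of SAP text and one merge of data already held. The downside is that the main outcome then mixes two survey sources. The ENGAGES-only analysis and the agreement table show whether that matters.

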### ***Hypothesis 1: Is EEG Guidance Intervention Associated with Reduced One-Year Mortality?***

*Patient Population:* Patients randomized to intervention or control (N = 1232)

*Primary Predictor Variable:* EEG guidance intervention

(X=0 for control or X=1 for intervention)

Intention to treat

*Outcome:* Mortality, with one-year follow up

- Any patient who is lost to follow up before one year will be right-censored at the time of last follow-up. (No assumptions are made about vital status after the date of last follow up.)

*Data Description Plan:* Kaplan-Meier curves, stratified by intervention group

*Analysis Plan:* Cox proportional hazards regression for one-year mortality

- Will perform unadjusted and adjusted analyses
- Will adjust for age, sex, American Society of Anesthesiologists (ASA) physical status classification (1-2 vs 3 vs 4-5), number of comorbid conditions, baseline poor functional capacity (<4 METS), history of falls (yes/no within previous 6 months), evidence of abnormal cognition (preoperative Short Blessed Test score > 4), surgery type (cardiac versus non-cardiac), length of anesthesia (Anesthesia Stop – Anesthesia Start)
  - o Multiple imputation may be used to address missing values of these variables

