1). The occurrence of burst suppression is the chief trigger for decreasing anesthetic administration in this protocol. An audible low-BIS alarm will be set at a threshold of 40, as there is an increased likelihood of epochs of EEG burst suppression below this value.⁴⁵ BIS values less than 40 will be a secondary trigger for decreasing anesthetic administration. Importantly, the EEG-guided protocol is suggestive rather than prescriptive. Clinicians should exercise judgment and might intentionally deviate from the protocol depending on the clinical situation. In both groups there will be an audible alarm for low volatile anesthetic agent (at 0.3 minimum alveolar concentration or at the clinician's discretion), which is standard practice at our institution to prevent intraoperative awareness. BIS EEG sensors will also be applied to patients in the control group for the purpose of data comparisons between groups, but when a patient is assigned to the control arm, practitioners will be blinded to all the EEG and BIS parameters, and will only see the signal quality index (SQI) of the EEG montage (Figure 5). EEG monitoring may continue to be acquired via continuous recordings of EEG, eye movements, and chin muscle activity for patients that are admitted to the ICU and step-down wards, or if the hospital room allows. Patients and research assistants assessing the study outcome measures (e.g., delirium assessments) will be blinded to the allocated intervention.

Figure 4: The anesthesia monitor is configured for the EEG-guided arm such that the raw electroencephalograph (EEG) waveform as well as the non-proprietary numerical values are displayed by the monitor, including the burst suppression ratio (SR) and the spectral edge frequency (SEF). The EEG filter is turned off so the low frequency slow delta waves (with a frequency of about 0.5 Hz.) are clearly visible. Turning off the filter allows EEG waves <2 Hz to be seen. The filter is a bandpass filter from 2 Hz to 70 Hz with a notch to eliminate 60 Hz alternating current electrical noise. With the filter off, the system has a bandwidth of approximately 0.25 Hz to 100 Hz.

Figure 5: The anesthesia monitor is configured for the control arm such all the EEG and BIS parameters are hidden, and only the signal quality index (SQI) of the EEG montage is visible.

Ensure practitioner fidelity to the EEG-guided protocol

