According to seven of nine criteria elaborated in the pragmatic-explanatory continuum indicator summary (PRECIS-2) tool¹¹¹, the ENGAGES trial is designed predominantly as a pragmatic rather than as an

during the first phase of the study, there will be structured education of clinicians to increase their familiarity and comfort with EEG-guidance of anesthesia. We therefore anticipate that practitioner familiarity with EEG will increase over the course of the study, although only basic knowledge regarding EEG analysis will be needed. Similarly, any anesthesia practitioner, regardless of their background or expertise, can apply the control (comparison) protocol. 5) Instructions on how to apply the EEG-guided protocol are flexible, offering practitioners discretion in deciding how to formulate and apply it. Although clinicians carrying out the EEG-guided protocol will use their own discretion in managing anesthesia, there is an expectation that less anesthesia will be administered in the EEG-guided arm and that the cumulative duration of EEG suppression will be less in the EEG-guided arm. During the first phase of the study, clinician adherence to the EEG-guided protocol will be evaluated and will partially inform the value of proceeding with the second phase of the study. Similar to the intervention arm, when patients are randomized to the control arm, anesthesia clinicians will have leeway to pursue their usual practice with minimal restrictions. There are some limitations in relation to anesthetic technique (e.g. based on potent volatile anesthetic), however these are consistent with current practice at our institution and more broadly. 6) For the primary intervention of the ENGAGES trial, participants will be anesthetized and will have no ability to impact adherence to the intervention. Therefore, this domain was left blank in the PRECIS-2 determination, as recommended¹¹¹. 7) Patients enrolled to the ENGAGES trial will be followed with more frequent visits and more extensive data collection than would occur in routine practice. 8) Incident delirium, the primary outcome of the study, is an objectively measured, clinically meaningful outcome to the study participants. The outcome can be assessed under usual conditions and typically does not rely on central adjudication. However, special training in rigorous delirium assessment is required. It is important to note that the abstraction of information of delirium from the medical records bolsters the pragmatic aspects of the trial, since this is an information source that is readily available at any hospital. 9) The analysis of the results will include all patients regardless of clinician compliance with the EEG-guided protocol (i.e. it will be an “intention-to-treat” analysis). The analysis will attempt to determine whether or not the EEG-guided protocol prevents postoperative delirium under the usual conditions, with all the noise inherent therein. Although in most respects the ENGAGES trial was judged to be pragmatic, this appraisal might have been biased as it was conducted by investigators associated with the study.¹¹²

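### Exploratory items 1-9 use one randomised arm as instrument for three exposures, so the IV results cannot show which exposure is responsible and are not evidence separate from Hypotheses 1-3

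*SAP*

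**What the plan says.** The SAP's Exploratory Analyses take three exposures in turn: "Is duration of intraoperative EEG suppression (minutes with suppression ratio > 1%) associated with mortality" (item 1), "Is duration of intraoperative BIS < 40 associated with mortality" (item 4) and "Is median intraoperative end-tidal anesthetic concentration value (measured in MAC) associated with mortality" (item 7). Each exposure is repeated for quality of life and for falls. Line (a) of each item is a covariate-adjusted model. Line (b) is the same sentence nine times: "Instrumental variable analysis will be used to account for the EEG intervention". The SAP names no instrument, estimator, first-stage model, exclusion restriction or rule for reading three parallel IV results.

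The one randomised variable is the arm, coded "X=0 for control or X=1 for intervention" under Hypothesis 1.

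The protocol section on the primary intervention says "The occurrence of burst suppression is the chief trigger for decreasing anesthetic administration in this protocol", and then "BIS values less than 40 will be a secondary trigger for decreasing anesthetic administration". The section on pragmatic elements records "an expectation that less anesthesia will be administered in the EEG-guided arm and that the cumulative duration of EEG suppression will be less" in that same arm.

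The SAP's opening lines grade p < 0.05 as suggestive and p < 0.005 as stronger evidence. They exempt no analysis.

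**The concern.** An IV analysis attributes an effect to an exposure only if the instrument reaches the outcome through that exposure alone (the exclusion restriction). Here one binary instrument is to serve three exposures, and the protocol describes an intervention meant to move all of them. The arm supplies one piece of information per outcome, while three exposure effects are unknown.

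The risk is misattribution. Suppose the arm improves quality of life through suppression only, or by some route that none of the three exposures captures. The IV results for the other exposures would then tend to reach significance too. Read under the SAP's grades, they would look like several supporting findings about depth of anesthesia, although they restate an arm comparison already made in Hypotheses 1-3.

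**Working it through.** **No stated figure to reproduce.** The documents give no number for the IV analyses. The nearest figure fixes the scale. The protocol's quality-of-life calculation assumes about 1,000 completers, a 0.5-point difference and SD 2.5, and claims more than 80% power. With 500 per arm, power = Φ(0.5 / (2.5 × √(2/500)) − 1.96) = Φ(3.162 − 1.960) = 88.5%, which agrees.

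**Counting.** Three exposures × four outcomes (mortality, VR-12 PCS, VR-12 MCS, falls) = 12 IV tests. There are four arm contrasts, one per outcome, all tested in Hypotheses 1-3. For each outcome there is one moment condition and three exposure effects, so the effects are not jointly identified.

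**Algebra.** With arm Z, covariates W and exposure X, the first stage is X̂ = a + πZ + cW. X̂ is linear in Z and W, so replacing Z by X̂ in an outcome model that already contains W only rescales the coefficient: β_IV = (arm effect on outcome) / π. This is exact for linear two-stage least squares (2SLS). It is also exact for logistic or Cox predictor substitution, given the same covariates and patients.

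**Numerical check, one simulated trial** (n = 1,000; only suppression affects the outcome; quality-of-life arm effect 0.3233, p = 0.0486):

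| Exposure | First stage π | First-stage F | 0.3233/π = IV estimate | Second-stage p | 2SLS Wald p |
|---|---|---|---|---|---|
| Suppression | −0.411 | 38 | −0.786 | 0.0486 | 0.028 |
| BIS < 40 | −0.216 | 10 | −1.495 | 0.0486 | 0.048 |
| MAC | −0.139 | 4 | −2.318 | 0.0486 | 0.088 |

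Predictor substitution gave the arm test's p value for all three exposures in the falls model (0.4912) and the mortality model (0.4108). Two-stage residual inclusion did not: p was 0.19-0.26 for falls and 0.39-0.43 for mortality.

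**How often a zero-effect exposure is flagged.** Setup: 2,000 trials per setting, n = 1,000, 1:1 allocation, two-sided 0.05, 2SLS Wald test, correlated exposures and an unmeasured confounder. The documents give no first-stage size, so the shifts below (exposure residual SD 1) are assumptions. Only suppression acts, and it carries a 0.5-point arm effect:

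| Shifts: suppression / BIS < 40 / MAC | Arm test rejects | BIS < 40 flagged (true effect 0) | MAC flagged (true effect 0) |
|---|---|---|---|
| 0.5 / 0.5 / 0.5 | 87% | 89% | 89% |
| 0.5 / 0.3 / 0.2 | 86% | 86% | 70% |
| 0.3 / 0.3 / 0.3 | 72% | 78% | 77% |
| 0.8 / 0.8 / 0.8 | 90% | 90% | 90% |

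Other cases:

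- Arm effect 0.25 points: the zero-effect exposures are flagged in 27-41%.
- A 0.5-point effect by a direct path, with no exposure acting: all three are flagged, in 67-94%.
- No arm effect: 1.4-4.9%.
- First-stage shift as weak as 0.1 (0.5-point arm effect): flagging falls to 15-31% across separate runs, and the correlation between the IV and arm z statistics falls to about 0.5.

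In the tabulated settings with an arm effect, including the 0.25-point and direct-path cases, the three Wald decisions agreed in 74-99.8% of trials. Agreement was lowest when first stages were weak and unequal.

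**The case against.** The strongest defence is that the three exposures may lie in series: the arm lowers anesthetic, which lowers suppression and low-BIS time, which affects outcome. Each exposure is then on every path, and all three exclusion restrictions can hold together. The protocol's wording, in which the EEG signals are triggers for giving less anesthetic, is compatible with this. A reader might infer that the three restrictions contradict one another; they conflict only if the exposures act by parallel paths, and the documents do not settle that. But the SAP asserts no serial chain, and even under one the data could not tell the exposures apart.

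A reader might also infer that every IV test is the arm test under another name, or that an inert exposure is flagged whenever the arm effect is significant. Neither follows. The rescaling is exact for the estimates described above, but the Wald test matches the arm test closely only when the first stage is strong. Residual inclusion, or a different analysis set because exposure data are missing, breaks the identity.

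Three further points stand. Per-minute and per-MAC estimates, their intervals and the first stages do differ by exposure. The items are labelled exploratory and ask about association. Hypotheses 1-3 and the line (a) models are unaffected. Even so, IV is a causal method, the SAP writes no caveat, and its evidence grades cover these tests.

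**Conclusion.** The concern holds as a defect of specification and interpretation in the exploratory section. On the only available reading of line (b), 12 IV tests rest on four arm contrasts and cannot separate suppression, BIS < 40 and MAC. Misattribution needs a real arm effect. With a 0.5-point effect and assumed shifts of 0.2 to 0.8, an inert exposure is flagged in roughly 70-90% of trials; with weaker first stages it is flagged less often, and without an arm effect error is not inflated. The percentages depend on the assumed shifts, exposure correlations and confounding. The identification failure does not. Two things are inferred because the SAP is silent: that the arm is the instrument, and that the estimator is 2SLS or predictor substitution. It would go too far to say that the SAP makes causal claims for each exposure, or that its main hypotheses are compromised.

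**What to change.** Amend line (b) of items 1-9 to:

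- name the randomised arm as the instrument and state the estimator for each outcome model;
- state the exclusion restriction for each exposure, acknowledge that the arm is expected to move all three, and report first-stage strength for each;
- say that the IV results for an outcome are one arm contrast rescaled, cannot show which exposure is responsible, and are not evidence separate from Hypotheses 1-3;
- say that the suggestive and stronger-evidence grades are not applied to them exposure by exposure.

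Any exposure-specific statement should rest on the line (a) models, labelled as associations.

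Keeping a single exposure for IV is optional. If that is done, its exclusion restriction needs its own argument. Suppression's role as the main trigger for lowering anesthetic is not one, because anesthetic exposure could affect outcome by other routes.

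The cost is SAP wording and fewer exposure-specific IV claims, which this design could not have supported. No new data are needed.
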